9.2.2 Serious adverse events (SAEs)

A serious adverse event is any untoward medical occurrence or effect that

- results in death;
- is life threatening (at the time of the event);
- requires hospitalisation or prolongation of existing inpatients' hospitalisation;
- results in persistent or significant disability or incapacity;
- is a congenital anomaly or birth defect; or
- any other important medical event that did not result in any of the outcomes listed above due to medical or surgical intervention but could have been based upon appropriate judgement by the investigator.

An elective hospital admission will not be considered as a serious adverse event.

The investigator will report all SAEs to the sponsor without undue delay after obtaining knowledge of the events, except for the following SAEs: there are no conditions to be considered based on swallowing a food supplement or eating

tomato soup or flebotomy that are likely resulting in a SAE within one week of consumption.

The sponsor will report the SAEs through the web portal *Onderzoeksportaal* to the accredited METC that approved the protocol, within 7 days of first knowledge for SAEs that result in death or are life threatening followed by a period of maximum of 8 days to complete the initial preliminary report. All other SAEs will be reported within a period of maximum 15 days after the sponsor has first knowledge of the serious adverse events.

9.2.3 Suspected unexpected serious adverse reactions (SUSARs)

Not applicable.

9.3 Annual safety report

Not applicable.

9.4 Follow-up of adverse events

All AEs will be followed until they have abated, or until a stable situation has been reached. Depending on the event, follow up may require additional tests or medical procedures as indicated, and/or referral to the general physician or a medical specialist. SAEs need to be reported till end of study within the Netherlands, as defined in the protocol.

9.5 Data Safety Monitoring Board (DSMB) / Safety Committee

Not applicable.

10. STATISTICAL ANALYSIS

Lycopene plasma concentration curves over time will be depicted in tables and in graphs in absolute and relative (compared to T0) amounts. Trends in changes over time will be interpreted, if needed based on background information on confounding parameters. There are no statistical calculations planned.

10.1 Primary study parameter(s)

Lycopene plasma concentration curves over time will be depicted in tables and in graphs in absolute and relative (compared to T0) amounts. Trends in changes over time will be interpreted, if needed based on background information on confounding parameters. There are no statistical calculations planned.

10.2 Secondary study parameter(s)

Lycopene plasma concentration curves over time will be depicted in tables and in graphs in absolute and relative (compared to T0) amounts. Trends in changes over time will be interpreted, if needed based on background information on confounding parameters.

There are no statistical calculations planned.

FFQ and food diary data will be reported descriptively.

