While the generally accepted opinion is that diets high in antioxidants are beneficial for suppressing and prevention of all cancers, and that they promote the overall health status of individuals, it may be difficult to change a life style that incorporates a healthy diet. Therefore in this study, we are searching for a parameter in body fluids that reflects the intake of healthy diet, and as such may motivate and sustain its continuous use (compliance marker). In case of prostate cancer we address lycopene as our target for reasons described above. Ideally, our lycopene related marker should reflect the short-term uptake of lycopene, and be based on a single dose consumption, in order to act as a direct feed-back to the consumers dietary action. Current methods of determination (see further) do not yet live up to point-of-care applications. There is, however, evidence that single dose consumption is reflected in the lycopene plasma concentration. In a trial in Italian consumers on lycopene kinetics on single dose consumption [5], a significant increase of plasma lycopene concentration of 40

nmol/l was observed above an individual base level (around 400 nmol/l), with a max concentration at 12 hours, and a normalisation after 48 hours after consumption of 15 mg of lycopene. Also a biomarker reflecting the adequate lycopene consumption of a medium long term (e.g. one week consumption) might provide a valuable asset for consumers. In a trial in Swiss male consumers on an 8-day intervention of 20 mg after lycopene depletion, the individual lycopene plasma concentration topped to a steady state of 1000 to 1500 nmol/l, while two weeks after the intervention (so during lycopene depletion) a plateau phase was obtained on a plasma concentration of 400-500 nmol/l [4], likely due to the release of lycopene from liver resources. We conclude that for consumer reasons the choice for a point-of-care testing of single dose lycopene is feasible, but restricted by current technology, and that feed-back on medium long term lycopene consumption is also feasible, as it is well reflected in plasma lycopene concentrations.

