Plasma lycopene concentrations show variation between individuals, and within individuals. It is unknown if and how much a single dietary intervention with lycopene from lycopene-rich vegetables like tomatoes alters the plasma concentration, and therefore can be used as a compliance marker.

As the bioavailability and plasma kinetics of lycopene is known to a limited extend (see studies above), a scheme for plasma determinations is followed according to previous marker (GABA, also found in tomatoes, serving as an exemplary study design) research from the same Wageningen group, including a wash out period of at least two weeks between interventions in the cross-over design [7].

- 2) Is a tablet lycopene with equivalent lycopene content as effective as a single dose dietary intervention regarding the change of plasma lycopene concentration?

Previous studies suggest equivalence, which might be of interest for consumers/patients.

- 3) Is the prior food consumption of individuals, as measured by dietary questionnaires, related to the plasma lycopene levels before and after lycopene intervention?

If an existing individual high intake of lycopene as analysed by a validated questionnaire would result in a high standard plasma lycopene concentration, or little response on single dose lycopene consumption, the subject might exclude for further supplementary lycopene consumption and life style changes.

Intervention: We have chosen a single dose of 40 mg lycopene as an intervention based on the following. Previously, in a dose escalating study to 90 mg lycopene daily in men with Research protocol

recurrent PCa after primary treatment, no effects were seen on the level of PSA, in contradiction to two studies conducted in men with metastatic PCa [8]. Also in high doses maintained for several weeks no toxicity was observed, while lycopene plasma levels corresponded with dietary dose. For chronic use, the daily dose of 30 mg is recommended based on a large review [9].

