2. OBJECTIVES

Primary Objective:

To determine whether a plasma lycopene concentration can serve as a response parameter after a single dose of dietary lycopene.

Secondary Objectives:

1. To determine if a food supplement tablet lycopene with equivalent lycopene content compared to a single dose dietary intervention provides identical plasma lycopene concentration responses compared to the dietary intervention.
2. To determine the influence of prior food consumption, as measured by dietary questionnaires, on plasma lycopene levels before and after lycopene intervention.

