4.4 Sample size calculation

Observational study obtaining individual lycopene concentration curves in plasma. It is anticipated that a measurable lycopene response will be seen in all participants. Based on the literature described in the introduction section it is hypothesized that in Dutch participants the plasma level of lycopene might be comparable to the Swiss population, that a single dose response to 40mg lycopene in combination with oil will provide a measurable response of plus 10% in all individuals. Therefore a sample size of two times five participants (10 participants in total) has been chosen.

Our pilot still needs to obtain an impression that responses are observed in all individuals, and to confirm that our HPLC-assay is an adequate technique. We will express that in

percentages of the group, such as: 'In xx percent the lycopene concentration increased more than 10% of the T=0 within 48 hours after intervention A'.

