8.1.2 Secondary study parameters/endpoints

1. Optimal time point of lycopene concentration response after single dietary intervention (hours, days).
2. Influence of prior food consumption on plasma lycopene levels before and after lycopene interventions, as measured by dietary questionnaires.

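### Section 10.2 plans no calculations, but the secondary objectives ask for a tablet-soup comparison and a diet-plasma relation, so neither can be answered as worded

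*Protocol*

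**What the plan says.** Section 2 sets two secondary objectives. The first asks whether the tablet "provides identical plasma lycopene concentration responses compared to the dietary intervention". Research question 2 in Section 1 asks the same in other words: whether the tablet is "as effective as a single dose dietary intervention regarding the change of plasma lycopene concentration". The second objective is "To determine the influence of prior food consumption, as measured by dietary questionnaires, on plasma lycopene levels before and after lycopene intervention".

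Section 8.1.2 lists the time point of the response and "Influence of prior food consumption on plasma lycopene levels before and after lycopene interventions, as measured by dietary questionnaires". It contains no tablet-soup endpoint.

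Section 10.2 plans tables and graphs of the concentration curves, absolute and relative to T0, with trends interpreted informally. It then states: "There are no statistical calculations planned". The same sentence stands in Sections 10, 10.1 and 10.3. On diet, Section 10.2 adds only: "FFQ and food diary data will be reported descriptively".

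**The concern.** The first secondary objective is a comparison and the second an association. The analysis section provides neither a contrast nor a measure of association. The design is a randomised AB/BA crossover, which gives a within-man contrast directly, yet none is planned.

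At stake is how the results will be read. With ten men, two sets of curves that look alike could be reported as identical while a sizeable difference remains compatible with the data. The diet question could likewise be settled by impression. Section 1 makes agreement with the food questionnaires one of the conditions for carrying lycopene into the follow-up prostate cancer study, so that answer will be used.

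**Working it through.** **Step 1: objectives against planned analysis.**

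- Tablet versus soup: objective in Section 2 and research question in Section 1; no endpoint in Section 8.1.2; curves only in Section 10.2.
- Prior diet and plasma lycopene: objective in Section 2; endpoint in Section 8.1.2 without a measure; diet data described separately in Section 10.2.
- The only numerical summary in the protocol is the Section 4.4 template, "In xx percent the lycopene concentration increased more than 10% of the T=0 within 48 hours after intervention A". It summarises one intervention and is not a contrast.

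**Step 2: precision of a within-man tablet-soup difference.** The protocol gives no SD, margin or precision target, so there is no figure of its own to reproduce.

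Inputs from the protocol:
- A single-dose study of 15 mg in Section 1 found a 40 nmol/l rise that "was observed above an individual base level (around 400 nmol/l), with a max concentration at 12 hours, and a normalisation after 48 hours".
- Samples at 0, 1, 3, 6, 12, 24, 48 and 72 h (Section 8.3); ten men, AB/BA (Section 8.2).

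Assumed:
- sample-to-sample CV 3%, 5% or 10%;
- correlation between successive samples 0 or 0.8, by sample order, so unequal gaps are treated alike;
- triangular rise, proportional to dose (40/15 = 2.67);
- sampling noise only.

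For a summary Σ w_j C_j − C_0 with contrast vector c and correlation matrix R:
- SD per period = 400 × CV × √(c′Rc)
- 95% half-width = t(0.975, 8 df) × √(2/10) × SD = 2.306 × 0.447 × SD = 1.031 × SD

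At CV 5%:
- Mean rise over 0-48 h (trapezoid): √(c′Rc) = 1.109 (independent) or 0.996 (0.8). SD = 22.2 or 19.9; half-width = 22.9 or 20.5 nmol/l. Expected rise = (½ × 48 × 40)/48 = 20, × 2.67 = 53.3 nmol/l. Half-width is 39-43% of the rise.
- Change at 12 h: √(c′Rc) = 1.414 or 1.087. SD = 28.3 or 21.7; half-width = 29.2 or 22.4. Expected rise = 40 × 2.67 = 106.7. Half-width is 21-27% of the rise.
- Mean rise over 0-72 h: half-width 22.7 or 21.3 against 13.3 × 2.67 = 35.6, that is 60-64%. Half the trapezoid weight (0.333 + 0.167) falls on the 48 h and 72 h samples, where the assumed signal is zero.

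Across CV 3% and 10%, the 0-48 h figure is 23-26% and 77-86%, and the 12 h figure 13-16% and 42-55%. Without dose scaling, all percentages are multiplied by 2.67; at CV 5% that gives 103-114% (0-48 h) and 56-73% (12 h).

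Cross-check on the ratio scale: with an assumed within-man SD of log response of 0.10, 0.20, 0.30 or 0.40, the 95% interval is the estimate multiplied and divided by 1.11, 1.23, 1.36 or 1.51.

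**Step 3: diet correlation, n = 10.** For Spearman r = 0.5, z = 0.549 and SE(z) = √((1 + 0.25/2)/7) = 0.401. The limits are 0.549 ± 1.96 × 0.401 = −0.237 and 1.335, which back-transform to −0.23 and 0.87. An observed correlation must exceed about 0.68 to exclude zero.

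**Step 4: timing of the second questionnaire.** It falls one week before the second dose, so 21 − 7 = 14 days after the first. Its recall is one month (Section 8.3), so it covers the first study dose.

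**Step 5: what the contrast compares.**
- Tablets: 2.5 × 15 = 37.5 mg against the stated 40 mg.
- Soup: at 8.4 mg per 100 g (Section 6.1), 40 mg needs 40/0.084 = 476 g of tomato, while 250 g would hold 21 mg. No concentration step is described. Other figures come closer: 5 kg (Section 5.1) over ten portions would be 500 g and 42 mg each, but the number of portions is not stated; the general 33 mg per 200 g of soup in Section 1 scales to 41 mg per 250 g.
- Olive oil (20 ml) is stated only with the soup, while Section 1 says that fat promotes absorption.

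**The case against.** The strongest reply is that this is a ten-man pilot, that Section 4.4 seeks only an impression, and that descriptive reporting is legitimate at this size. That stands. A reader might infer that the lack of hypothesis tests is itself a defect; the documents do not support that.

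A reader might also infer that the plan yields no effect size at all. That goes too far. Section 10.2 plans tables as well as graphs, and in a crossover these show each man's values under both products. What is missing is a named summary and its uncertainty.

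It can also be said that an interval does not rescue the first objective, because no sample size shows identity and the protocol gives no margin. This is right, and it is why rewording comes first. The imprecision also depends on the chosen summary: the 0-72 h percentages are more than twice those for the 12 h change, so they should not be quoted as the precision of the trial.

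Finally, one might fault Section 10 for not repeating the Section 4.4 responder percentage. That is a cross-reference matter and does not bear on the secondary objectives.

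Deferral to a separate analysis plan is no answer, because the protocol is not silent. It states that no calculations are planned.

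**Conclusion.** The mismatch is in the text and should be corrected. Followed as written, Section 10.2 gives no estimate with uncertainty for the tablet-soup difference and no measure for the diet relation, so neither secondary objective is answered as worded. The primary objective is not affected. The diet half carries more decision weight; Section 1 presents the tablet question only as of possible interest to consumers and patients.

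The sizes in the working rest on the assumed CV, serial correlation, triangular shape and dose proportionality, and they leave out any true variation between men in the product difference. What does not depend on those assumptions is that identity cannot be shown without a margin. The diet interval depends only on n = 10 and the observed correlation.

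A tempting further reading is that a tablet-soup interval would settle equivalence at equal lycopene content. The documents do not support this, because their stated amounts do not reconcile and the oil is stated for one product only.

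**What to change.** 1. In Section 2, replace 'identical' with estimating the difference between tablet and soup, and list that difference in Section 8.1.2.
2. In Section 10.2, replace the sentence that rules out calculations with two estimates labelled exploratory, without tests:
   - the within-man tablet-minus-soup difference, with a period term and 95% interval, in one prespecified baseline-corrected summary whose window matches the expected response, for example incremental AUC over 0-48 h;
   - the rank correlation, with 95% interval, of lycopene intake from the first questionnaire with the first T0 and with the man's mean post-dose rise. The first questionnaire is used because the second covers the first study dose.
3. State that the contrast compares the two products as given. Reconcile the tablet amount, the soup amount and the olive oil statement across Sections 1, 3, 5.1, 6.1 and 8.3 before it is read as a comparison at equal lycopene content.

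If only curves are wanted, reword both secondary objectives as descriptive. That costs less but gives up both answers.

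The cost is protocol wording and a few hours of analysis, with no new samples or visits. The downside is wide intervals and a diet correlation that will probably be inconclusive.

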10.3 Other study parameters

Lycopene plasma concentration curves over time will be depicted in tables and in graphs in absolute and relative (compared to T0) amounts. Trends in changes over time will be interpreted, if needed based on background information on confounding parameters.

There are no statistical calculations planned.

10.4 Interim analysis

No interim analysis is planned.

11. ETHICAL CONSIDERATIONS

11.1 Regulation statement

The study will be conducted according to the principles of the Declaration of Helsinki and in accordance with the Medical Research Involving Human Subjects Act (WMO) and other relevant guidelines, regulations and Acts, such as the GDPR.

11.2 Recruitment and consent

After reading the flyer, interested volunteers can contact the principal investigator. Through email or mail the volunteer will receive a patient information leaflet. After careful consideration and time to ask questions, volunteers can decide to participate yes/no. Signed informed consent forms can be handed over or send back by mail to the principle investigator or a member of the research team. The dedicated member of the research team will document and store the signed informed consent forms.

11.3 Objection by minors or incapacitated subjects

Not applicable.

11.4 Benefits and risks assessment, group relatedness

Consuming tomato soup, taking the dietary supplement and completing the food frequency questionnaire and the food diary do not pose any significant risks. The blood drawings carry a small risk of infection and may be somewhat painful.

11.5 Compensation for injury

The sponsor/investigator has a liability insurance which is in accordance with article 7 of the WMO.

The sponsor (also) has an insurance which is in accordance with the legal requirements in the Netherlands (Article 7 WMO). This insurance provides cover for damage to research subjects through injury or death caused by the study.

The insurance applies to the damage that becomes apparent during the study or within 4 years after the end of the study.

11.6 Incentives

Participants will receive a remuneration of €50,- per visit cycle (cycle A, cycle B – or cycle B, cycle A), €100,- in total for participation in the study. Furthermore, participants will receive reimbursement of their travel costs.

12. ADMINISTRATIVE ASPECTS, MONITORING AND PUBLICATION

12.1 Handling and storage of data and documents

After reading the flyer, interested volunteers can contact the principal investigator who will provide them with an informed consent form. Once men have returned a signed informed consent form they will be assigned a study number and be included in a study database (Castor). The designated researcher from Erasmus MC will have access to the identification list, all other databases shall only contain the study number assigned to an individual participant.

In communication with the Wageningen University, who is responsible for determining the lycopene level, analysing the outcomes of the FFQ and the food diary, the study number of participants will be used. The researchers at Erasmus MC will receive a file with the outcomes of the analysed lycopene levels of all participants as well as the results of the FFQ and the food diary.

Per blood draw, one tube of 6ml EDTA blood will be drawn from participants. Processed material will initially be stored at Erasmus MC. When all blood samples have been collected, half of the material per blood drawing will be send to the Wageningen University. The other half of the material will be stored at Erasmus MC as a back-up, and can be used in case something went wrong with transporting the material to the Wageningen University the first time.

12.2 Monitoring and Quality Assurance

Monitoring is part of a broader quality control system and an essential instrument for the quality assurance of research that is subject to WMO. It serves to verify that the rights and wellbeing of the research subjects are protected, that the study data are reported accurately and are fully verifiable in source documents, and that the conduct of the study is in accordance with the approved protocol/amendment (s), with ICH-GCP and with the relevant legal requirements.

Monitoring will be performed in accordance with applicable law and regulation, the NFU Guideline 'Quality assurance of research involving human subjects' and the NFU risk classification (negligible risk/'verwaarloosbaar risico'). The monitor will have an independent role in relation to the study, i.e. he/she will not have any involvement in the set-up of the study, the conduct of the study and the interpretation of the results. In accordance with the ICH-GCP guidelines, the monitor must have direct access to the

investigator's study- and source documentation in order to verify compliance with the study protocol and check the data recorded in the CRFs for consistency.

Monitoring is executed according to Erasmus MC policy standard operating procedures for monitoring. At the beginning of the study a study specific monitoring plan will be written and approved by the sponsor. The investigator agrees to cooperate with the monitor to ensure that any problems detected in the course of these monitoring visits are resolved. Prior to subject screening an initiation meeting will be held with all participating sites to discuss the protocol and procedures and to train the site. After data collection is complete, all eCRF queries have been answered and closed, a close out visit will be conducted. The investigator should be made aware that trial – and source documents for this study should be readily made available to regulatory authority or health authority inspectors.

